## 5. RESOURCES AVAILABLE TO CONDUCT THE HUMAN RESEARCH

- *Explain the feasibility of meeting recruitment goals of this project and demonstrate a potential for recruiting the required number of suitable subjects within the agreed recruitment period*
  - *How many potential subjects do you have access to?*
- *Describe your process to ensure that all persons assisting with the trial are adequately informed about the protocol and their trial related duties and functions*

Northwell Health employs over 72,000 employees, a vast number of whom are between the ages of 45-75 years. As an organization committed to the promotion of wellness as a means of decreasing disease and disability, our colleagues in both the Employee Wellness Department and Occupational Health Services have agreed to support promotion of this study. Northwell social media groups and electronic communications remain a rich resource for research participant recruitment. Our team has demonstrated exceptional success in virtual, personalized trial recruitment using these employee recruitment pathways, and boasts high levels of participant satisfaction with virtual participation in personalized trials.

All study personnel are fully trained in Human Subjects Protections and HIPAA/Privacy protections. All engaged staff members are listed on the IRB and compliant with trainings and attestations as required by the Northwell Health Human Research Protection Program. Additionally, staff will be required to participate in weekly meetings with the Principal Investigator, and an additional weekly meeting with the Project Manager, in order to stay informed about the study protocol, staff duties and functions, and to answer any questions that come up within the group. Staff will have daily access to the Project Manager, Director of Clinical Research, and Principal Investigator to answer any protocol questions they may have outside these established weekly meetings.

## 6. RECRUITMENT METHODS

- *Describe the source of potential subjects*

- *Describe the methods that will be used to identify potential subjects*
- *Describe any materials that will be used to recruit subjects. A copy of any advertisements (flyers, radio scripts, etc.) should be submitted along with the protocol.*
- *If monetary compensation is to be offered, this should be indicated in the protocol*

Since the proposed study will take place virtually, potential participants may be recruited from any Northwell facility.

Potential participants may be recruited via the following avenues:

- Email advertisement through employee communication channels, within the Northwell Health network.
- E-mail advertisements through existing email lists from those who previously expressed an interest in participation in a Personalized Trial with the Center for Personalized Health
- Flyers, shared within the Northwell Health network.
- Northwell Health employee social media (Facebook) site.

Potential participants will be Northwell Health employees who are community-residing, 45-75 years old, healthy, report that they walk regularly without health/safety issues, and express an interest in participating in a Personalized Trial to increase their walking by a minimum of 2000 steps five to seven days each week. Study activities are divided into phases. Participants in the first four preliminary phases (non-interventional) will receive 5,000 points credited to their “Northwell My Recognition” account. In the 5th or intervention phase, involving ten weeks of study participation, participants will receive a pay card valued at \$100 for completing all study requirements. Additionally, they will be able to keep their Fitbit valued at \$150.

## 7. ELIGIBILITY CRITERIA

- *Describe the characteristics of the subject population, including their anticipated number, age, ranges, sex, ethnic background, and health status. Identify the criteria for inclusion or exclusion of any subpopulation.*
- *Explain the rationale for the involvement of special classes of subjects, such as fetuses, pregnant women, children, prisoners or other institutionalized individuals, or others who are likely to be vulnerable. You cannot include these populations in your research, unless you indicate such in the protocol*
- *Similarly, detail exclusionary criteria: age limits, special populations (minors, pregnant women, decisionally impaired), use of concomitant medications, subjects with other diseases, severity of illness, etc.*

**Inclusion Criteria:** Northwell Health employee

-At least 45 years of age

-Able to speak and comprehend English  
-Community dwelling  
-Report they are in good general health, walk regularly and have never been informed by a clinician that it was not advisable/safe to participate in a low intensity walking program  
-Owns and can regularly access a smartphone capable of receiving text messages  
-Owns and can regularly access an email account

Exclusion Criteria:

-Not employed by Northwell Health  
-Less than 45 years of age or greater than 75 years of age  
-Unable to speak/comprehend English  
-Have self-reported poor health, limited mobility and/or have been advised by a clinician not to increase their low-intensity walking  
-Pregnancy  
-Previous diagnosis of a serious mental health condition or psychiatric disorder such as bipolar disorder

## 8. NUMBER OF SUBJECTS

- *Indicate the total number of subjects to be accrued locally. If applicable, distinguish between the number of subjects who are expected to be pre-screened, enrolled (consent obtained), randomized and complete the research procedures.*
- *If your study includes different cohorts, include the total number of subjects in each cohort.*
- *If this is multisite study, include total number of subjects across all sites.*

We expect to pre-screen and enroll up to 180 potential participants in this study. Up to 60 participants will be recruited across the four preliminary (brief duration) phases. Up to 60 participants will be randomized to the 10 week personalized trial, first undergoing a 2 week baseline monitoring of their walking behavior, followed by 8 weeks of monitoring their walking in response to each of the four behavioral change techniques (2 weeks per technique).

## 9. STUDY TIMELINES

- *Describe the duration of an individuals participation in the study*
- *Describe the duration anticipated to enroll all study subjects*
- *The estimated date of study completion*

The initial phases of study participation will involve either a single session via a virtual interaction (electronic meeting, 1:1 interview or electronic correspondence) or remote evaluation of study message content and frequency over the course of five days. The last study phase will involve a total of 10 weeks of study participation: activity tracking using a Fitbit activity monitor for 10 weeks, and

responding to behavior change strategy prompts and surveys delivered via text message to a secure link for 8 weeks. At the end of the 10 week intervention period, a report containing the individual's responsiveness to each BCT will be sent to the participant, along with a satisfaction survey.

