receive up to four text message prompts per day. They will complete a measure of self-efficacy (i.e. confidence in their ability to walk without stopping) and a ‘satisfaction with BCT’ survey once every two weeks. At the end of their trial, participants will receive a satisfaction survey and a summary of their observed data to help them learn more about their responses to the four behavioral change techniques and to inform investigators as to the feasibility of N-of-1 study design for future research and clinical applications.

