#### **4. OBJECTIVE(S)/SPECIFIC AIMS AND HYPOTHESES**

- *A concise statement of the goal(s) of the current study.*
- *The rationale for and specific objectives of the study.*
- *The goals and the hypothesis to be tested should be stated.*

The specific aims of the study include:

-Eliciting and incorporating participant feedback in the development of required content and study procedures for implementation of a personalized, virtual

interventional trial to enhance low-intensity walking using behavioral change techniques

- Determine the feasibility of conducting a virtual, randomized control trial using participant selected behavioral change techniques
- Examine the novel individual-level heterogeneity of treatment effect made possible by the crossover, personalized trial design, and pool results across patients to efficiently estimate the overall efficacy of the four behavioral change techniques in increasing low-intensity walking by 2,000 steps, 5 days per week.
- Assess the relationship between individual behavior change techniques and walking self-efficacy.
- Elicit participant attitudes and opinions toward using Personalized Trials to help inform their personal wellness strategy

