In the four preliminary phases (with up to 10 participants each in phase 1,3, 4 and up to 30 participants in Phase 2), virtual focus groups and/or 1:1 discussions will be held to answer questions and elicit feedback about the comprehensibility of behavior change strategy descriptions, special study website content and videos, the ability to receive “sample” study messages in home and work settings, the virtual informed consent process, and study tools with attention toward for clarity and ease of use.

Potential participants for the Personalized Trial Participants will be sent a secure message with the start date of their baseline period, as well as a review of what to expect during onboarding to the study. They will be mailed an initial study kit including a Fitbit device. A PDF copy of their electronically signed consent form will be made available to all participants via N1Thrive/REDCap secure messaging. Potential participants will be asked to download the Fitbit app to their smart phone. No more than 20 participants will be permitted to begin on the same day.

The baseline period will take place over the course of two weeks. During the baseline period, potential participants will be asked to wear their Fitbit for 10 ours per day and also while they are sleeping, as tolerated and to acknowledge receipt of a daily text message that is not an activity prompt. Baseline participants will be instructed to sync their Fitbit device by opening the Fitbit app on their phone at least every two days.

Individual adherence to Fitbit wear and to survey responses will be assessed in order to determine which individuals progress to intervention. Adherence to Fitbit wear will be defined as recorded activity of greater than 10 hours a day. Text message adherence will be defined as responding to a given text message. Baseline participants that do not achieve at least 80% adherence of Fitbit wear and text responsiveness the baseline period will be withdrawn from the study. Those that maintain at least 80% adherence will be randomized to one of their selected behavior change techniques to begin their pilot personalized trial. Participants who are randomized to receive intervention sequences will receive email confirmation including their protocol timeline. Enrollment will continue until up to 60 participants have been randomized.

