#### Intervention Delivery

This pilot study will use text messages to deliver four behavioral change techniques identified in Michie et al.’s (2011) paper which identified those BCTs associated with influencing change in physical activity behavior. These BCTs were updated to align with current BCT definitions using Michie et al.’s (2013) Taxonomy of Behavioral Change Techniques. A list of BCTs is provided as an appendix to this protocol. Participants will also receive **bi-weekly surveys** to assess their satisfaction with the given BCT and walking self-efficacy. BCTs will be provided to participants in a randomized crossover design with each BCT delivered individually in one of four 2-week blocks. The order in which participants receive BCTs will be randomized with the randomization order determined by the study

statistician. Prior to BCT delivery (i.e. every two weeks) participants will be sent information/BCT descriptions the day before they start their new BCT so that they understand the differences between the four BCTs for their personalized trial. For instance, BCT descriptions may include:

BCT Name	Definition	Sample Text Message Prompt
Goal Setting Behavior	Set or agree on a goal defined in terms of behavior to be achieved	Set the goal of being more active today. Record your goal
Action Planning	Prompt detailed planning of performance of behavior (must include a setting frequency, duration, and intensity)	“It’s Tuesday. Walk 2,000 steps from 10am -11am this morning.”
Self-Monitoring of Behavior	Establish a method for person to monitor and record their number of active periods based on their Fitbit	“It’s time to check your FitBit dashboard and view how active you have been today.”
Feedback on Behavior	Monitor and provide informative or evaluative feedback on performance of the behavior (e.g. form, frequency, duration, intensity)	“You met your goal yesterday. You walked 2,000 steps more than baseline.”

Participants may receive additional text messages to those outlined above with important reminders to sync their data as needed.

Upon completion, participants in the personalized trials phase will receive an individual report that demonstrates their walking responses in relation to their assigned BCTs and a satisfaction survey to obtain feedback about their personalized trials experience.

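### No walking self-efficacy score is scheduled before the first technique, so the self-efficacy aim can compare techniques with each other but cannot show a change from the starting level

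*Combined protocol and SAP*

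**What the plan says.** Section 4 lists as an aim: "Assess the relationship between individual behavior change techniques and walking self-efficacy". It names no contrast.

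Section 2 says of participants: "They will complete a measure of self-efficacy (i.e. confidence in their ability to walk without stopping", paired with a BCT-satisfaction "survey once every two weeks". Section 11, under Intervention Delivery, places both in the same bi-weekly surveys, "to assess their satisfaction with the given BCT and walking self-efficacy".

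Section 9 gives two different windows: "activity tracking using a Fitbit activity monitor for 10 weeks", but "responding to behavior change strategy prompts and surveys delivered via text message to a secure link for 8 weeks". The 8 weeks match the four 2-week BCT blocks.

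The baseline is described in Section 8 as "first undergoing a 2 week baseline monitoring of their walking behavior". Section 11 asks baseline participants to wear and sync the Fitbit and "to acknowledge receipt of a daily text message that is not an activity prompt". It then refers to survey responses when judging who may progress, but the definition that follows counts only replies to text messages.

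Section 12 specifies a GEE model for steps. It gives no analysis for self-efficacy.

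**The concern.** Every intervention block carries a BCT. If the only self-efficacy scores come from those blocks, none reflects the participant without a BCT. The trial could say that one technique goes with higher self-efficacy than another. It could not say that any technique, or all four together, raised or lowered self-efficacy from where it began.

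This matters for reading a null result. The measure is confidence in walking without stopping, and participants must already walk regularly, so uniformly high scores are plausible. Without a starting value, the pilot could not tell scores that were high from the outset from a similar improvement under all four techniques. The missing score cannot be collected once a participant's first block has begun.

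**Working it through.** There is no figure in the plan to reproduce. Section 12 chooses 60 participants for feasibility and states no alpha, power, effect size or SD. The question is what can be estimated.

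**Inputs.** Survey window: 8 weeks (Section 9). Survey interval: 2 weeks (Section 2). Blocks: four, one BCT each, in random order (Section 11, Intervention Delivery). Baseline: 2 weeks, always first (Section 8).

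**Count.** Scores per participant: 8 / 2 = 4, all under a BCT. Four BCTs plus baseline make 5 conditions and 5 × 4 / 2 = 10 pairwise contrasts. Of these, 4 × 3 / 2 = 6 are between BCTs and 10 − 6 = 4 involve baseline. Those 4 have no data on the baseline side.

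**Common shift.** Write the mean score under technique k as μ + c + d_k, where μ is the starting level, c a shift shared by all four techniques, and d_k what is specific to k. A between-BCT contrast is (μ + c + d_j) − (μ + c + d_k) = d_j − d_k, so c cancels. The data carry only the sum μ + c, and cannot separate its parts.

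**Rank check.** The design matrix has an intercept and 4 BCT indicators, over all 24 BCT orders, with three ways of handling time. A contrast is estimable if adding it as a row leaves the rank unchanged.

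| Scores | Time term | Rank / parameters | BCT minus no BCT | BCT minus BCT |
|---|---|---|---|---|
| As scheduled | none | 4 / 5 | not estimable | estimable |
| As scheduled | linear | 5 / 6 | not estimable | estimable |
| As scheduled | categorical | 7 / 8 | not estimable | estimable |
| Plus one baseline score | none | 5 / 5 | estimable | estimable |
| Plus one baseline score | linear | 6 / 6 | estimable | estimable |
| Plus one baseline score | categorical | 8 / 9 | not estimable | estimable |

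The last row fails because baseline always occupies the first period: being in baseline and being in that period are the same indicator.

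**Price of the trend.** Put baseline at time 0 and the blocks at times 1 to 4 (mean 2.5). In units of residual variance per participant, BCT minus baseline has variance 1 + 1 = 2.00 with no time term. A linear slope is learned from the spread of block times, 2.25 + 0.25 + 0.25 + 2.25 = 5, and carried back 2.5 units. That adds 2.5² / 5 = 1.25, for a total of 3.25. The ratio is 3.25 / 2.00 = 1.625, or about 1.6. BCT minus BCT stays at 2.00.

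**The case against.** The case on the other side has two parts.

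**The schedule may already include a baseline score.** Section 11 mentions survey responses during baseline. Section 2 does not confine the two-weekly interval to the intervention weeks, so 10 weeks could give five surveys. The 8 weeks in Section 9 might cover only BCT surveys. The day within a block is not stated, so a first survey could precede the first prompt.

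None of these readings places a self-efficacy score in baseline. Section 11 makes its survey wording operational only as replying to a text. The self-efficacy item travels with satisfaction with the given BCT, which cannot be answered before a BCT is given. No other section schedules a questionnaire in baseline. What stands is that the gap is inferred from the schedule, since no sentence excludes a baseline score, and that the Section 11 wording needs clarifying.

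**The aim may not need a baseline.** It asks for a relationship and names no change from baseline, so between-BCT differences can meet its literal wording. The baseline comparisons in Section 12 concern feasibility and steps. Section 10 does not name self-efficacy as an endpoint. All of this stands. It limits the priority of the point, but not the fact that a common shift would go unseen.

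**Conclusion.** On the schedule as written, no self-efficacy measure precedes the first BCT, and the contrast of BCT with no BCT is not estimable under any of the three time models. Between-BCT contrasts are estimable in all three. This is structural and does not depend on the sample size. It rests on reading the bi-weekly surveys as falling within the BCT blocks.

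A reader might infer more than the documents support:

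- That the self-efficacy aim fails, or is only half answered. The aim names no contrast, so what is lost is specifically any statement about change from the starting level.
- That one baseline score would fully recover the four missing contrasts. Baseline always comes first, so they would be uncontrolled before-after comparisons that depend on an assumed form for time. The between-BCT contrasts remain the randomized ones.
- That the added burden is exactly 60 surveys. Sixty is the cap on those randomized, after the 80% adherence screen. A survey in baseline also reaches people later withdrawn, and the documents do not say how many enter baseline.

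This is a cheap improvement of lower priority, since it concerns a listed aim outside the named primary and secondary endpoints of a feasibility pilot.

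**What to change.** 1. Send the same self-efficacy survey once at the end of the 2-week baseline, before the first BCT description, which goes out the day before block 1. Omit the BCT-satisfaction items. Amend Sections 9 and 11 to match.
2. In Section 11, say what survey responses means in baseline.
3. In Section 12, state a self-efficacy analysis with one score per block, the baseline score as reference, and an explicit time assumption (none or linear). The same-day covariance described for steps does not carry over directly to one score per block. Label the baseline contrasts as before-after and the between-BCT contrasts as randomized.

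This gives self-efficacy the same kind of before-after reference that steps already have. The cost is one short automated survey for each person entering baseline, possibly more than 60 in all, and a minor consent wording change. It uses the existing platform and needs no extra staff.

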## 10. ENDPOINTS

- *Describe the primary and secondary study endpoints*
- *Describe any primary or secondary safety endpoints*

This study is a feasibility pilot whose primary objective is to assess the acceptability, scalability of implementation and participant satisfaction with a personalized trial methodology using behavior change techniques to promote low-intensity physical activity. Secondary endpoints include pooling personalized trial results to assess efficacy of BCTs utilized to promote walking behavior.

## 11. PROCEDURES

- *Include a detailed description of all procedures to be performed on the research subject and the schedule for each procedure.*
- *Include any screening procedures for eligibility and/or baseline diagnostic tests*
- *Include procedures being performed to monitor subjects for safety or minimize risks*
- *Include information about drug washout periods*
- *If drugs or biologics are being administered provide information on dosing and route of administration*
- *Clearly indicate which procedures are only being conducted for research purposes.*
- *If any specimens will be used for this research, explain whether they are being collected specifically for research purposes.*
- *Describe any source records that will be used to collect data about subjects*
- *Indicate the data to be collected, including long term follow-up*

Potential participants will self-identify as Northwell employees who are 45-75 years of age, community-dwelling, are in good general health, report walking regularly, and have never been advised by a clinician that it is unsafe/not advisable for them to increase low-intensity walking, and are interested in increasing their low-intensity walking by a minimum of 2000 steps 5 out of 7 days each week. Those who are interested in participating in this pilot study will be directed to an initial screening survey that includes questions pertaining to inclusion and exclusion criteria. Those who are determined to be eligible will receive a secure message with a link to an electronic participant information sheet (preliminary study phases) or the electronic informed consent form (Personalized Trial participants). Before being able to sign and submit the consent form, potential personalized trial participants must demonstrate understanding of the protocol by correctly answering 4 questions pertaining to the information presented in the consent form. Contact information (name, age, Northwell email, cell phone number and service provider) will be obtained from all consented participants.

In the four preliminary phases (with up to 10 participants each in phase 1,3, 4 and up to 30 participants in Phase 2), virtual focus groups and/or 1:1 discussions will be held to answer questions and elicit feedback about the comprehensibility of behavior change strategy descriptions, special study website content and videos, the ability to receive “sample” study messages in home and work settings, the virtual informed consent process, and study tools with attention toward for clarity and ease of use.

Potential participants for the Personalized Trial Participants will be sent a secure message with the start date of their baseline period, as well as a review of what to expect during onboarding to the study. They will be mailed an initial study kit including a Fitbit device. A PDF copy of their electronically signed consent form will be made available to all participants via N1Thrive/REDCap secure messaging. Potential participants will be asked to download the Fitbit app to their smart phone. No more than 20 participants will be permitted to begin on the same day.

The baseline period will take place over the course of two weeks. During the baseline period, potential participants will be asked to wear their Fitbit for 10 ours per day and also while they are sleeping, as tolerated and to acknowledge receipt of a daily text message that is not an activity prompt. Baseline participants will be instructed to sync their Fitbit device by opening the Fitbit app on their phone at least every two days.

Individual adherence to Fitbit wear and to survey responses will be assessed in order to determine which individuals progress to intervention. Adherence to Fitbit wear will be defined as recorded activity of greater than 10 hours a day. Text message adherence will be defined as responding to a given text message. Baseline participants that do not achieve at least 80% adherence of Fitbit wear and text responsiveness the baseline period will be withdrawn from the study. Those that maintain at least 80% adherence will be randomized to one of their selected behavior change techniques to begin their pilot personalized trial. Participants who are randomized to receive intervention sequences will receive email confirmation including their protocol timeline. Enrollment will continue until up to 60 participants have been randomized.

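### Recruitment on a stated 2,000-step aim, with a Feedback text that presupposes a goal, blurs the Goal Setting and Feedback contrasts with baseline

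*Combined protocol and SAP*

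**What the plan says.** **Before baseline.** Section 6 expects participants who "express an interest in participating in a Personalized Trial to increase their walking by a minimum of 2000 steps five to seven days each week". Section 11 repeats this as self-identification, ahead of screening and consent: people who "are interested in increasing their low-intensity walking by a minimum of 2000 steps 5 out of 7 days each week". The efficacy part of the aims in section 4 is framed in the same terms, "increasing low-intensity walking by 2,000 steps, 5 days per week".

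**During baseline.** Section 11 asks participants to wear the Fitbit, sync it at least every two days and "acknowledge receipt of a daily text message that is not an activity prompt". It says nothing about keeping to usual activity.

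**During the blocks.** The Intervention Delivery part of section 11 gives each technique alone in its own two-week block, in random order. It defines Goal Setting as "Set or agree on a goal defined in terms of behavior to be achieved". The sample texts are:
- Goal Setting: "Set the goal of being more active today. Record your goal"
- Feedback: "You met your goal yesterday. You walked 2,000 steps more than baseline"
- Action Planning: "Walk 2,000 steps from 10am -11am this morning"

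**Analysis.** Section 12 takes baseline as the comparator for the four techniques. Section 10 makes pooled efficacy secondary to feasibility, acceptability and satisfaction.

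**The concern.** A contrast with baseline isolates a technique only if that technique is absent from baseline and no other technique is present in its block. Two features of the plan put this in doubt.

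First, participants know a numeric walking target before baseline, and nothing asks them to wait. Anyone who starts on it early raises the reference against which Goal Setting is judged. The same baseline is the reference in the Feedback text.

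Second, the sample Feedback text tells the participant that a goal was met. Where Feedback comes before Goal Setting, the Goal Setting block cannot be the source of that goal.

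At stake are the pooled estimates for these two techniques, the comparison between them, and the individual report that tells each participant how they responded to each technique. Early action on the aim may well differ between people, so individual contrasts could be distorted by different amounts.

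**Working it through.** The plan states no effect size, standard deviation or power figure behind its 60 participants, so there is no figure to reproduce. The check is of the logic of the contrasts.

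**Order.** Four techniques can be ordered in 4! = 24 ways. Goal Setting precedes Feedback in 12 and follows it in 12. In the second 12, a goal mentioned in the Feedback block must come from the recruitment aim, from another text or from the Feedback text itself. In the first 12, a goal kept from the earlier Goal Setting block is a further possible source.

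**Additive model.** Let
- mu = usual walking
- g = effect of holding a step goal
- s = added effect of the Goal Setting texts
- f = effect of feedback
- p = share of g already active in baseline (0 to 1)
- q = share of g active in the Feedback block (p to 1)

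Mean steps per day are then:
- Baseline: mu + p·g
- Goal Setting block: mu + g + s
- Feedback block: mu + q·g + f

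The contrasts are:
- Goal Setting − baseline = s + (1 − p)·g. Intended: s + g. Bias: −p·g.
- Feedback − baseline = f + (q − p)·g. Intended: f. Bias: +(q − p)·g.

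**Limiting cases.**
- p = 1 (goal fully active from baseline on, so q = 1): Goal Setting shows only s, and Feedback shows f without bias.
- p = 0, q = 1 (no goal in baseline, Feedback text brings it in fully): Goal Setting shows s + g without bias, and Feedback shows f + g.
- 0 < p < 1, q = 1: both contrasts are biased, Goal Setting downward and Feedback upward.
- q = p (the Feedback text adds no goal content): Feedback is unbiased and only Goal Setting is affected.

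**Illustration.** The values are assumed and come from no document: g = 1,000, s = f = 500 steps per day, q = 1. Intended contrasts: Goal Setting 1,500, Feedback 500.

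| p | Goal Setting − baseline | bias | Feedback − baseline | bias |
|---|---|---|---|---|
| 0 | 1,500 | 0 | 1,500 | +1,000 |
| 0.25 | 1,250 | −250 | 1,250 | +750 |
| 0.5 | 1,000 | −500 | 1,000 | +500 |
| 0.75 | 750 | −750 | 750 | +250 |
| 1 | 500 | −1,000 | 500 | 0 |

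With q = 1 the two absolute biases always add up to g, because p·g + (1 − p)·g = g. The difference Goal Setting − Feedback is s − f = 0 in every row, against an intended s + g − f = 1,000. In this example the two techniques look identical although one was set to be three times the other (1,500/500 = 3).

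**Other techniques.** A goal share that stays constant from baseline into the Self-Monitoring block cancels. The Action Planning sample names 2,000 steps, so if that brings in goal content, its contrast behaves like the Feedback one.

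**The case against.** The strongest reply is that interest in a study's aim is not the Goal Setting technique. A reader might infer that every participant agrees a 2,000-step goal at enrolment and that Goal Setting therefore runs from baseline onward. The documents do not support this. Participants are described as interested. The step target is not among the inclusion criteria in section 7 or the statements to be confirmed at web screening in section 23. Goal Setting as sampled is a prompted goal that the participant records, and nothing like it happens in baseline. This reply stands: p above zero is plausible, but it is an inference.

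A reader might also conclude that neither effect can be isolated. That does not follow. A goal held constantly from baseline cancels from the Feedback contrast, and with no goal in baseline the Goal Setting contrast is intact. Only partial activation biases both. Nor would all four estimates fall by the same amount: that requires an aim that raises baseline and then stops acting in the blocks.

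Finally, the texts are samples, and section 2 says the preliminary phases will settle message content. The final Feedback wording may differ. This makes the correction easy but does not remove the need for it, because nothing in the plan requires Feedback to be free of goal content.

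**Conclusion.** The point holds as a limited one. The aim is disclosed before baseline, baseline carries no usual-walking instruction, and the sample Feedback text presupposes a goal despite the one-technique-per-block design. The Goal Setting contrast is attenuated by whatever share of the goal effect is already acting in baseline. The Feedback contrast is inflated by whatever goal content its text adds beyond that share.

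The documents do not give the size. Under the additive model each bias lies between zero and g. The conclusion rests on three assumptions: g is above zero, effects add, and any early action on the aim continues into the blocks. If feedback works differently for people who hold a goal, the Feedback contrast is also conditional on holding one.

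The primary objective is feasibility and efficacy is secondary, so this is a cheap improvement and no threat to the pilot's main purpose.

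**What to change.** 1. Add to the baseline instructions in section 11: *keep to your usual walking during these two weeks*. This lowers p.
2. Make the Feedback text informative only, for example *Yesterday you walked X steps; your two-week baseline average was Y*, with no mention of a goal being met. This brings q towards p. The protocol's own definition of Feedback allows informative as well as evaluative content, so the technique is still delivered.
3. State in sections 4 and 12 that the Goal Setting contrast estimates prompted goal setting and recording on top of a known study aim. If Action Planning keeps its 2,000-step figure, say there that the figure is part of that technique's content.

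The target should not be withheld from recruitment or consent material, since participants should know the study's aim.

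The cost is one instruction, one message template and a sentence or two in the plan. The small downside is that Feedback loses its evaluative wording. One limit remains: when the usual-walking instruction ends, the known aim may act in all four blocks. A share common to the blocks cancels between techniques but not against baseline, and the sentence in section 12 should say so.
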